#### 4.0 ELIGIBILITY/EXCLUSION CRITERIA

##### Inclusion Criteria

1. Must have pathologically confirmed squamous metaplasia or squamous dysplasia documented by autofluorescence bronchoscopy within the preceding 60 months.
2. Must be a former or current smoker.
3. Must be between the ages of 40-79 years.
4. Participants must have a total granulocyte count of  $> 1.5 \times 10^9 /L$ , and a platelet count of  $> 100 \times 10^9 /L$
5. Participants must have adequate renal function with a calculated creatinine clearance of  $> 60 \text{ ml/min}$  from a serum specimen collection at baseline using the Cockcroft-Gault formula:

$$eCr = \frac{(140 - \text{Age}) \times \text{Mass (in kilograms)} \times [0.85 \text{ if Female}]}{72 \times \text{Serum Creatinine (in mg/dL)}}$$

I 90206 Amendment # 18

6. Participants must have a 24-hour calcium concentration that is  $\leq$  300mg/ 24 hours as measured by 24-hour urine collection at baseline.
7. Participants must have a total bilirubin less than the upper limit of normal and transaminases/alkaline phosphatase  $\leq$  2.5 x IULN.
8. Participants must have an albumin of  $\geq$  2.5 g/dl.
9. Participants must have an ionized serum calcium within normal limits.
10. Must meet ECOG performance status criteria of 0-1 (0 = fully active, must be able to carry out all pre-disease activities without restriction; 1 = restricted in physically strenuous activity, but ambulatory and able to carry out work of a light or sedentary nature).
11. Must be willing to attend all scheduled study visits, complete all study questionnaires, and allow biological specimen collection including a bronchoscopy within 3-4 months after enrollment into the study
12. Women of child-bearing potential (i.e. women who are pre-menopausal or not surgically sterile) must use acceptable contraceptive methods (abstinence, intrauterine device (IUD), oral contraceptives or double barrier device) and must have a negative serum or urine pregnancy test within 1 week prior to beginning treatment on this trial. Sexually active men must also use acceptable contraceptive methods. Pregnant or nursing patients are excluded from participating in this trial. Contraceptive use needs to be continued at least 1 month after the trial has ended.
13. Must be able and willing to sign an informed consent approved by the Institutional Review Board (IRB).

### **Exclusion Criteria**

1. Subjects with life-threatening medical conditions that would preclude bronchoscopy, including: acute cardiac failure, which is unstable despite medication use; uncontrolled hypertension; uncontrolled diabetes mellitus; or unstable coronary artery disease.
2. Patients with severe metabolic disorders that would preclude administration of calcitriol.
3. Evidence of current disease with lung cancer or head and neck cancer.
4. Patients may have a prior history of lung cancer or head and neck cancer treated with curative intent, provided that there has been no evidence of disease (NED) for  $> 1$  year. The qualifying AF bronchoscopy must be negative for malignancy.
5. Patients with a history of any other malignancy within 3 years except non-melanoma skin and cervical CIS.
6. Patients with a history of renal lithiasis within the last 5 years or patients with evidence of kidney stones on entry evaluation.
7. Patients with impaired renal function CRCL  $\leq$  60 mL/min.
8. Patients with hypercalcemia (using ionized calcium).
9. Subjects taking calcium supplements. If subjects are willing to discontinue these supplements, there must be a 2-month wash out period before enrollment.
10. If patients are routinely taking a multivitamin supplement, they will be asked to continue the supplement as long as the amount of vitamin D in the supplement is not in excess of the RDA (recommended daily allowance). If they are not taking a multivitamin supplement, they will be asked to not start supplementation while on study.
11. Subjects with a known hypersensitivity to calcitriol.
12. Subjects taking thiazides (which can decrease urinary excretion of calcium).
13. Patients taking phenobarbital, digitalis, thiazides or ketoconazole.

I 90206 Amendment # 18

14. Patients taking digoxin or patients who are susceptible to calcium-related dysrhythmias.
15. Patients taking bile acid binding drugs (such as cholestyramine and colestipol).
16. Patients taking danazol.
17. Patients taking aluminum-based antacids.
18. Oral ketoconazole or other azole antifungals.
19. Women who are pregnant or lactating are excluded from the study.
20. No known allergies to tree nuts (i.e. almonds).

Study Flow  
Chart

Procedure	Screening	MONTH 1							MONTH 2							MONTH 3							Follow up (1)
		Day 1	Day 2	Day 14	Day 15	Day 16	Day 28	Day 1	Day 2	Day 14	Day 15	Day 16	Day 28	Day 1	Day 2	Day 14	Day 15	Day 16	Day 28	Day 1	Day 2	Day 14	Day 15
Eligibility Interview	X																						
Informed Consent	X																						
Complete Physical Exam	X																						
Medical History Update	X																						
Toxicity Evaluation (Nurse)	X	X	X				X															X	X
Spirometry and FEV1	X																						
Renal Ultrasound	X																						
24 hour urine collection (2)	X																						
Assessment of Supplement Use	X																						
Chemistry Panel (3) and ionized calcium	X		X			X	X															X	X
Hematology Panel (3)	X		X			X	X															X	X
25-OH vitamin D	X																						X
Dose 45 mcg Calcitriol (QOW)		X			X			X									X		X		X		
PK Samples for Calcitriol (4)		X	X																				
AF Bronchoscopy	X																						X

Phone call dose reminder				X		X			X		X		X			
Phone call toxicity check						X	X	X	X	X	X	X	X	X	X	
Blood for future studies ( 5)	X	After 24-48 hours and every 3 months while on treatment if the patient signs the DBBR consent														

1. Follow up labs will be done only for patients with toxicities at the time of cessation of the treatment.

2. 24 hour urine will be collected for the measurement of creatinine and calcium concentration.

3. **Chemistry Panel:** Chloride, CO2, Potassium , sodium, urea nitrogen, Glucose, Calcium, ionized Serum Calcium, Creatinine, Total Protein, Albumin, Aspartate aminotransferase, Alanine aminotransferase, osmolality serum, Anion gap, BUN/Creatinine ratio, Pregnancy test within 1 wk of enrollment (screening only).

**Hematology:** CBC will be monitored every other week in the first month then monthly until the end of the intervention.

The blood collection will occur on the day after the pills are taken. Vitamin D levels (25-OH-Vitamin D) will be drawn twice.

4. PK/PD sampling: Blood will be taken for PK/PD at the following time points, predose, .5, 1, 3, 5 and 24 (day 2) hours post dose.

5. Blood samples will be drawn before treatment, 24-48 hours following initiation of treatment and every three months during treatment alongside clinical blood draws, and frozen for future correlative studies. Samples will be drawn in phlebotomy and sent to the RPCI Data Bank and Bio Repository for storage per DBBR Standard Operating Procedures for Vitamin D Trial banking participants

I 90206 Amendment # 18

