## 7. TREATMENT PLAN

**Informed consent:** All patients prior to enrollment in this study will sign an Informed Consent in conformity to Federal and Institutional guidelines.

I 90206 Amendment # 18

**Calcitriol Administration:** The subjects will receive 45mcg /QOW of oral calcitriol capsules one day every other week. Subjects will take one capsule QOW for 3 months, for a total of 6 capsules. Subjects will be supplied with 3 months' worth of capsules (6 capsules) dispensed by the UB pharmacy.

When the patient has signed the informed consent, eligibility confirmed they will be scheduled to take their first dose and have PK/PD studies. A fax will be sent to [name], RPh at the Suny at Buffalo, Buffalo School of Pharmacy. . This fax will include: A completed prescription for the calcitriol (the original will be sent to [name] by courier that week) and the date of the patient's next scheduled visit.

Her complete contact information is:

[name], RPh, MS  
SUNY at Buffalo, Buffalo School of Pharmacy  
School of Pharmacy and Pharmaceutical Sciences  
[name]  
South Campus  
[name]  
[contact]  
[contact]

Upon receipt of the fax, [name] will label 6 individual blister packs for the calcitriol capsule 45mcg/cap. The label on each blister pack will include the following information:

SUNY at Buffalo, Buffalo School of Pharmacy  
New Drug Investigational use  
Calcitriol 45 mcg/capsule  
[name] RPh [name] Date

The 6 blister packs will be placed in an amber zip-lock bag and labeled with patient specific information. The label on each ziplock bag will include the following information:

SUNY at Buffalo, Buffalo School of Pharmacy  
Research Pharmacy  
[name] [contact] RPh: [name]

Subject's Name	Subject #	Fill Date
Subject's Address		

Take one capsule on an empty stomach (at least one hour before or two hours after meals) and drink approximately 4 cups of liquids in addition to your usual intake in the day of taking the pill and for the next two days as directed by project protocol.

Quantity: 6 blister paks  
Calcitriol 45mcg/capsule

I 90206 Amendment # 18

In case of an emergency, please contact Roswell Park Cancer Institute [contact]) and ask to speak to the Department of Medicine physician on call.

"Caution: New Drug--Limited by Federal (or United States) law to investigational use."

An auxiliary label "Keep in Refrigerator Do not Freeze" will be placed on the amber ziplock bag.

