The labeled calcitriol capsules will be sent by courier to Roswell Park and delivered to the Investigational Drug Service (IDS) where the capsules will be held until the patient returns to the clinic to start the trial. The PK/PD studies will start at time 0 and then the patient will take the first capsule. The PK/PD studies will be carried out as described in following sections.

**Calcitriol Formulation and Dispensing:** In each size 3 opaque capsule there will be 200 microliters of solution containing:

- 45 mcg Calcitriol
- 0.1% of each BHT and BHA (Concentration PCCA uses in their product 12000 nanograms/ml) in Almond oil as the vehicle.

The blister packs are heat sealed and placed in an amber ziplock bag to protect the capsules from sunlight.

Storage: After the completion of the PK/PD studies on Day 0, the patients take the blister pack home and store it in the refrigerator until two weeks later when they take another capsule.

Stability: Shelf life surveillance studies of formulated capsules are ongoing. Current data indicates calcitriol is stable for at least 5 years at room temperature when protected from light.

Method of Administration: Capsules should be taken once every other week. Subjects should take calcitriol on an empty stomach (at least one hour before or two hours after meals) and drink approximately 4 cups of liquids in addition to their usual intake in the day of taking the pill and for the next two days.

**8. Specimen and Data Collection and Processing:** A complete smoking history will be collected as per the clinic routine.

**Measurement of Plasma Vitamin D:** Blood samples for calcitriol determination will be sent to the PK/PD facility at RPCI for analysis. Patients will be coming into to have blood draw the day after taking the tablet. Plasma samples will be separated from 4 ml of blood collected in EDTA tubes for plasma calcitriol measurements. The samples will be centrifuged at 1400rpm at 4°C for 10 minutes and stored at -80°C until assayed.

I 90206 Amendment # 18

[figure not shown]

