#### **Drug Information**

The calcitriol will be supplied by:

PCCA Professional Compounding Centers of America.  
[name]  
[name]

The Product Formulation involves making a solution of the following:

Calcitriol 22.5mg  
Butylated Hydroxytoluene NF(BHT) 100mg  
Butylated Hydroxyanisole NF(BHA) 100mg  
in 100 mls of Almond Oil NF

Calcitriol (1, 25-dihydroxycholecalciferol) is the biologically active form of vitamin D. It is commercially available as an oral formulation of calcitriol designed specifically for high-dose, intermittent administration. In this protocol it will be studied in individuals at high-risk to develop lung cancer.

Because of the substantial preclinical data documenting the potent anti-cancer activity of calcitriol, clinical studies were conducted in various solid tumors with the currently marketed formulation of calcitriol using various routes and regimens. While efficacy was suggested in

I 90206 Amendment # 18

several studies, hypercalcemia was dose limiting in these studies. Moreover, plasma levels did not reach those that would be predicted to have anti-cancer activity.

Investigators discovered that intermittent dosing with calcitriol permits substantial dose escalation. The maximum dose of calcitriol tested was 2.8 µg/kg PO. Plasma calcitriol reached a plateau at doses  $\geq$  0.5 µg/kg PO at levels predicted to be associated with anti-cancer activity without causing dose limiting hypercalcemia. The safety of 0.5 µg/kg calcitriol PO qw was supported by clinical data in over 70 subjects with prostate cancer in three Phase 2 studies. The efficacy of calcitriol was suggested by open-label studies in subjects with AIPC when the drug was administered as either a single agent or in combination with docetaxel.

A Phase 1, multicenter, open-label, dose escalation study of DN-101 was carried out to evaluate the safety, tolerability, and PK of DN-101 (another formulation of calcitriol) in 38 subjects with advanced malignancies. An initial dose of up to 165 µg DN-101 PO was not associated with DLTs, so the MTD was not determined. The MTD for repeat weekly dosing in this study was defined as 45 µg PO qw based on the occurrence of transient, asymptomatic Grade 2 hypercalcemia in two subjects who were treated at 60 µg PO qw for nine weeks. The PK of DN-101 was linear and predictable; there was no evidence of saturation of absorption.

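### Exclusion criterion 20 on tree-nut allergy is worded as a requirement, so its literal meaning is reversed, while every capsule is filled with an almond-oil solution

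*Combined protocol and SAP*

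**What the plan says.** The protocol gives its eligibility criteria twice, in the Abstract and in section 4.0. In both, item 20 stands under "Exclusion Criteria" and reads "No known allergies to tree nuts (i.e. almonds". The wording and the position are the same each time.

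On the study drug, section 7 (Calcitriol Formulation and Dispensing) states: "In each size 3 opaque capsule there will be 200 microliters of solution containing" 45 mcg of calcitriol and two antioxidants, "in Almond oil as the vehicle". Section 9 (Drug Information) describes the bulk solution as 22.5 mg of calcitriol with the same antioxidants "in 100 mls of Almond Oil NF". On exposure, section 7 says: "Subjects will take one capsule QOW for 3 months, for a total of 6 capsules".

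The only other allergy item in either list is exclusion item 11: "Subjects with a known hypersensitivity to calcitriol". None of the 13 inclusion criteria mentions allergy.

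**The concern.** An exclusion list is normally applied as *excluded if true*. Applied that way, item 20 excludes a patient with no nut allergy and lets through a patient with one. That is the opposite of what an almond-oil capsule calls for.

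The same wording appears in both lists, so neither can be used to correct the other. Item 11 does not fill the gap, because it names the active substance and not the vehicle. The label text set out in section 7 identifies the capsules as calcitriol 45 mcg and does not mention almond oil. Section 7 also has patients take the remaining capsules home after the first dose. Section 5.0 refers to participating sites, so a shared understanding at one clinic may not reach everyone who screens patients.

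What is at stake is an avoidable exposure of an allergic participant, in a study whose purpose is to establish safety in people without cancer.

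**Working it through.** The plan gives no statistical figure on this point, and the point depends on no error rate, power or sample size. The check compares the texts and adds one piece of arithmetic on the capsule fill.

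**1. Literal effect of item 20 as an exclusion**

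| Patient | Is the statement in item 20 true? | Result if true means excluded |
|---|---|---|
| No known tree-nut allergy | Yes | Excluded |
| Known almond allergy | No | Not excluded by item 20 |

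**2. Is the list uniform in form?** Mostly, but not entirely. Item 11 names the disqualifying condition directly. So do items 3 and 18, which, like item 20, are fragments without a verb. Item 4 is different, being a permission: "Patients may have a prior history of lung cancer or head and neck cancer treated with curative intent", on stated conditions. Item 10 is an instruction about multivitamin use. Items 4 and 10 are full sentences whose direction is clear from their own words. Item 20 is a bare negated fragment, and its direction depends on which list it is read in.

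**3. Does another criterion cover the vehicle?** Item 11 is limited to calcitriol, and the inclusion list is silent. Item 20 is therefore the only written criterion on nut allergy.

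**4. Is the whole capsule fill the almond-oil solution?** The inputs are 22.5 mg in 100 mL (section 9), and a 200 microliter fill with 45 mcg per capsule (section 7).

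- Concentration: 22.5 mg / 100 mL = 22,500 mcg / 100 mL = 225 mcg/mL.
- Content of one fill: 225 mcg/mL × 0.2 mL = 45 mcg.

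This equals the stated capsule strength, so the 200 microliter fill is the almond-oil solution described in section 9.

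- Exposure over the course: 6 capsules × 0.2 mL = 1.2 mL of that solution per participant.

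The two formulation passages agree with each other. Item 20, read literally, is what conflicts with them.

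**The case against.** The strongest reply is that nobody would misread it. Taken literally, item 20 would exclude every patient without a known nut allergy, which no screener would do. *No known allergies* is a familiar way of stating a requirement, and the vehicle explains why the line is there. Items 4 and 10 show that the list already contains lines that cannot be applied mechanically as exclusions. Screening also includes an eligibility interview and a medical history, and the first capsule is taken at the clinic with blood sampling out to 5 hours. Consent pages are not available, so what patients are told about the vehicle cannot be judged.

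Most of this stands. It shows that the intent can be recovered and that item 20 is not the only occasion on which an allergy could come to light. It does not make the text correct. The mixed form of the list is a reason for care, because a reader cannot apply one rule to every line.

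A reader might be tempted to go further in three ways, none of which the documents support:

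- **That allergic patients would be enrolled.** The wording permits it if read literally. Nothing shows that it would happen.
- **That the eligibility checklist is wrong.** No such form is in the documents, and it may be worded correctly.
- **That a vehicle reaction would distort the interim analysis.** Only grade 3-4 toxicities, or grade 2 toxicities lasting more than two weeks, count, so a milder or shorter reaction would not. One qualifying event in 20 still meets the rule of at most 1. Missing that rule means recruiting to 40, not rejecting the null hypothesis. The documents give no rate for such reactions, so no size can be put on the effect. The same argument would apply to any extra event from any cause.

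**Conclusion.** The point holds as a wording error in an operative safety criterion, and it should be corrected. As written in both eligibility lists, item 20 states the reverse of what the formulation implies, and no other written criterion covers nut allergy.

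Its size is modest: one line, repeated once, with an intent most readers would recover. It is an internal inconsistency and not a flaw in the design. The sample size of 40, the interim rule (at most 1 toxicity in 20) and the final rule (8 or more in 40 rejects) do not depend on it.

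The conclusion rests on the two lists and the formulation text alone. It assumes nothing about how often nut allergy occurs in this population, how screeners behave, or what the consent form says.

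**What to change.** Reconcile item 20 in the Abstract and in section 4.0 with the almond-oil formulation in sections 7 and 9. Either of two edits does it:

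- keep it in the exclusion list and state the condition directly, for example *Known allergy to tree nuts (e.g. almonds)*; or
- move the existing sentence, unchanged, to the inclusion list.

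Make the same edit in both places. The present text uses *i.e.*, which equates tree nuts with almonds. If the line is reworded, the sponsor should confirm which scope is meant. Then check that any eligibility form built from the list agrees with the corrected wording.

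The cost is one line in two places and one check of a form. No analysis, sample-size or monitoring text needs to change.

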**Procedures for Toxicity Monitoring and Reporting:** The study nurse will assess potential toxicities during each phone call. If a subject reports changes in any of these symptoms, they will be documented as an AE and graded according to CTCAE 4.0. If the patient reports an AE of  $\geq 3$  grade, it will be reported to the PI or the treating physician to determine if they need to be evaluated at Roswell Park. The complete toxicity information will be reported to the medical director, [name], at the time of continuing review. Reports regarding toxicity, patient safety, and study progress will be submitted to the RPCI Institutional Review Board (IRB), FDA and to the NCI at the end of the study. The risks and side effects that have been reported to be associated with calcitriol include:

Likely Side Effects: those that may occur in approximately 10% - 30% of persons who receive this drug.	

• Most of the side effects described with calcitriol are related to elevations of calcium referred to as hypercalcemia (33%).

• Side effects related to high calcium can occur which include, kidney and bladder stones, weakness, dehydration, constipation, muscle aches, nausea, vomiting.

---	---

Unlikely Side Effects: those that occur in approximately 5% to 9% of persons who receive this drug.
	

• Cardiac arrhythmia (disorders of the regular rhythmic beating of the heart), high or low blood pressure.

• Headache, irritability, seizure (rare), somnolence (sleepiness), psychosis (inability to think clearly).

• Pruritus (itching of the skin), erythema (reddening of skin), multiforme (allergic reaction that occurs in response to medications).

• Hypermagnesemia (excess magnesium), hyperphosphatemia (high level of phosphate in blood), polydipsia (excessive thirst).

• Anorexia, constipation, metallic taste, nausea, pancreatitis, vomiting, xerostomia (dry mouth).

• Elevated liver function tests

• Bone pain, myalgia (muscle pain), dystrophy (weakness of muscles), soft tissue calcification

• Conjunctivitis (pink eye), photophobia (sensitivity to light)

• Polyuria (increased urination)

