Enrollment and treatment in a Phase 2 study of DN-101 in subjects with MDS has been completed. DN-101 was well-tolerated in the 37 subjects treated in this study. The study was closed to further enrollment when the Simon optimal two-stage analysis, which allowed an early study stop if the true rate of erythroid response was  $\leq$  30%; did not demonstrate the pre-specified number of responses for allowing continuation of the study.

**Risks to Subjects Participating in Clinical Studies of Calcitriol Observed Risks:** In monotherapy studies in subjects with malignancies, calcitriol has been well-tolerated. Low grade hypercalcemia (generally Grade 1) was the most commonly reported adverse event (AE) in 22% of subjects. Two of 6 subjects treated with 60 µg DN-101 weekly in the Phase I study and 3 of 37 subjects with MDS treated with 45 µg DN-101 weekly developed transient Grade 2 hypercalcemia. Other commonly reported AEs of low grade (Grade 1) include fatigue (14%), nausea (6%), increase in alanine aminotransferase (ALT) (5%), increase in serum creatinine (5%), hyperglycemia (5%), and anorexia (5%). Three different subjects reported a Grade 3 hyponatremia, proteinuria, or hypercholesterolemia, and one subject reported a Grade 4 hypercholesterolemia.

**Adverse Events Related to Calcitriol:** Based on the available safety data, the following treatment emergent AEs classified by participating Investigators as possibly or probably related to calcitriol have been reported for subjects treated with calcitriol in clinical studies. Most of these AEs were Grade 1 or 2; calcitriol -related Grade 3 or 4 AEs were rare.

1. ***Blood and lymphatic system disorders:*** anemia NOS, leukopenia NOS, neutropenia, thrombocytopenia, disseminated intravascular coagulation
2. ***Ear and labyrinth disorders:*** fortification spectra, ear congestion
3. ***Eye disorders:*** glaucoma NOS, conjunctivitis, lacrimation increased, vision blurred

4. **Gastrointestinal disorders:** abdominal pain NOS, constipation, diverticulitis NOS, dyspepsia, nausea, vomiting NOS, diarrhea NOS, stomatitis, abdominal pain upper, loose stools, dry mouth, cheilitis, retching
5. **General disorders and administration site conditions:** asthenia, fatigue, pain NOS, chest discomfort, lethargy, edema NOS, edema peripheral, infusion site reaction, mucosal inflammation NOS, pyrexia
6. **Hepatobiliary disorders:** hyperbilirubinemia
7. **Infections and infestations:** pneumonia NOS, oral candidiasis

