#### Risks Warranting Further Discussion:

1. **Hypercalciuria:** Many subjects treated with calcitriol develop hypercalciuria (elevated urine calcium) but acute nephrolithiasis has been very rare. The risk of nephrolithiasis due to hypercalciuria is minimized by increasing fluid intake.
2. **Hypercalcemia:** Hypercalcemia has been identified as the DLT in non-clinical and clinical studies of calcitriol, and occasional subjects taking calcitriol have had Grade 1 or 2 hypercalcemia. In the Phase 1 study of calcitriol in subjects with advanced malignancies, transient asymptomatic hypercalcemia (Grade 2) occurred in two subjects who received 60 µg calcitriol PO qw for nine weeks. The risk of hypercalcemia is minimized by increasing fluid intake, monitoring serum calcium, evaluating symptoms of hypercalcemia, excluding certain medications or supplements, and excluding subjects with a history of cancer-related hypercalcemia. Long-standing hypercalcemia may result in hypercalcemic nephropathy (interstitial

nephritis), a disease characterized by loss of distal tubule and collecting duct function, a reduction in glomerular filtration rate, and tubulointerstitial damage. Early recognition is important because damage can often be arrested or even reversed with discontinuation of the offending agent. Therefore, periodic monitoring of serum creatinine is recommended for subjects receiving high-dose calcitriol, including calcitriol. The interstitial nephritis seen in the 28-day repeated dose toxicity study of calcitriol in dogs was consistent with hypercalcemic nephropathy.

3. **Transient Renal Insufficiency:** Occasional subjects have had elevations of BUN or serum creatinine, or decreased creatinine clearance while taking calcitriol. The risk of renal toxicity due to calcitriol is minimized by excluding subjects with  $\geq$  Grade 2 elevations of serum creatinine and monitoring renal function during clinical studies with calcitriol.
4. **Hyperuricemia:** The possibility that calcitriol causes hyperuricemia cannot be excluded at this time. In the Phase 2/3 AIPC study (Study DN101-002), Grade 3 or 4 hyperuricemia was reported for two subjects (1.6%) in the group treated with calcitriol and docetaxel; hyperuricemia was not reported for subjects treated with docetaxel and placebo.

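### The scheduled chemistry panel omits two liver tests that eligibility requires and four analytes the protocol names as risks, so scheduled testing would miss silent abnormalities in them

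*Combined protocol and SAP*

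**What the plan says.** The Study Flow Chart schedules a chemistry panel at screening and on treatment. Section 5.0 places the on-treatment draws at Day 2, Day 16 and the ends of Months 2 and 3. Footnote 3 spells the panel out: chloride and CO2, then "Potassium , sodium, urea nitrogen, Glucose, Calcium, ionized Serum Calcium, Creatinine", then "Total Protein, Albumin, Aspartate aminotransferase, Alanine aminotransferase, osmolality serum, Anion gap, BUN/Creatinine ratio", plus a pregnancy test at screening only.

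The other safety tests are a blood count ("CBC will be monitored every other week in the first month then monthly until the end of the intervention") and a urine collection that the chart marks at screening only ("24 hour urine will be collected for the measurement of creatinine and calcium concentration").

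Inclusion criterion 7, identical in the Abstract and Section 4.0, reads in part "Participants must have a total bilirubin less than the upper limit of normal" and goes on to cap transaminases and alkaline phosphatase at 2.5 times the upper limit.

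The primary endpoint in the Abstract is the number of patients with a Grade 3-4 toxicity or a Grade 2 toxicity lasting over two weeks. Section 12 tests the same quantity. Neither limits it to particular analytes, and grading follows CTCAE version 4.

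**The concern.** There are two separate problems.

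First, an eligibility criterion sets limits on two liver tests that the schedule does not order, and no other source for those results is named.

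Second, the endpoint is wider than the scheduled measurements. The protocol itself names laboratory abnormalities that the panel would not show, and several of these can be symptomless. At stake is how a low count is read. This trial exists because the FDA asked for toxicity evidence in people without cancer. Both the early stop (1 or fewer toxicities in 20 patients) and non-rejection at the end (7 or fewer in 40) are outcomes in which few toxicities count in favour of the regimen. If an analyte was never tested, a reader of the final report could take that silence as evidence of safety.

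**Working it through.** The plan gives no figure on this point. The check is a comparison of passages, followed by an illustration of direction.

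**Step 1. Named abnormality against scheduled test.**

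| Analyte | Where the protocol names it | In footnote 3? |
|---|---|---|
| Total bilirubin | Criterion 7; Section 9, related adverse events | No |
| Alkaline phosphatase | Criterion 7; Section 5.0 also lists raised liver function tests in general | No |
| Phosphate | Section 5.0 side-effect table; Section 9, related adverse events | No |
| Magnesium | Section 5.0 side-effect table | No |
| Uric acid | Section 9, related adverse events and risks for further discussion | No |
| Cholesterol | Section 9, observed risks and related adverse events | No |
| Urine protein | Section 9, observed risks and related adverse events | No urine protein test is scheduled |
| Calcium, ionized calcium | Section 9, named dose-limiting toxicity | Yes |
| Creatinine, urea nitrogen, sodium, potassium, glucose, albumin, AST, ALT | Section 9 | Yes |

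The blood count and the screening urine for creatinine and calcium close none of these gaps.

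**Step 2. Direction.** A symptomless abnormality in an untested analyte cannot enter the count. Compared with testing it, the count stays the same or falls; it cannot rise.

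**Step 3. What the documents offer on size.**

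- Section 5.0 puts raised magnesium and phosphate in a row headed about 5% to 9%. Taken at face value, each is 0.05 × 40 = 2 to 0.09 × 40 = 3.6 patients. The row gives no grade, so the share reaching the endpoint is unknown.
- Section 9, on monotherapy in subjects with malignancies, says: "Three different subjects reported a Grade 3 hyponatremia, proteinuria, or hypercholesterolemia, and one subject reported a Grade 4 hypercholesterolemia". That is four events, of which only hyponatremia is on the panel. No denominator is attached to them.
- Section 9 gives 1.6% (two subjects) for Grade 3-4 hyperuricemia, in patients on calcitriol plus docetaxel.

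None of these converts to a rate of missed endpoint events at this dose and schedule in this population.

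**Step 4. Illustration of direction only.** Let p be the assumed true rate and m the assumed share of patients whose only qualifying event is in an untested analyte. The observed rate is e = p(1 − m). Under the Section 12 rule (continue if at least 2 of 20, reject if at least 8 of 40):

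P(reject) = Σ over a = 2 to 20 of P(X₁ = a) × P(X₂ ≥ 8 − a), and P(early stop) = P(X₁ ≤ 1), with X₁ and X₂ independent Binomial(20, e).

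With p = 25%:

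| m | e | Patients missed, 40 × p × m | P(reject) | P(early stop) |
|---|---|---|---|---|
| 0 | 0.250 | 0 | 0.813 | 0.024 |
| 10% | 0.225 | 1 | 0.701 | 0.042 |
| 20% | 0.200 | 2 | 0.557 | 0.069 |
| 30% | 0.175 | 3 | 0.396 | 0.112 |

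With p = 20%, P(reject) runs 0.557, 0.429, 0.301 and 0.186 over the same values of m. The rule is sensitive to one or two uncounted patients, but both p and m are assumptions and the documents support no particular value of m.

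**The case against.** The strongest reply is that the panel covers what matters most. Hypercalcemia, the named dose-limiting toxicity, is measured, and so is renal function. Section 9 describes calcitriol-related Grade 3-4 events as rare. Which secondary analytes to follow is partly judgement. All of that stands, and it is why uric acid and cholesterol are left to the sponsor.

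A reader might also infer more than the documents support:

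- **That patients failing the liver criterion could be enrolled.** Criterion 7 is mandatory, and Section 7 has eligibility confirmed before the first dose is scheduled. A patient without a bilirubin result could not be confirmed. The defect is an unscheduled test with no named source.
- **That these toxicities cannot be graded or counted, or will be recorded as absent.** No text treats an unmeasured analyte as normal. Toxicity is sought by telephone around each dose and at nurse visits, reported events of Grade 3 or above go to a physician, and prompted tests are not barred. Only silent abnormalities escape.
- **That three of four severe laboratory events would be missed here.** The four events in Section 9 have no denominator and come from patients with malignancies; the regimens specified there are weekly, not every other week. One was proteinuria, which added serum assays would not detect.
- **That 1.6% is a calcitriol-alone rate of severe hyperuricemia.** The patients also received docetaxel, and the protocol says only that a causal role cannot be ruled out.

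A further fair objection is that more assays could push the count the other way. No eligibility criterion limits phosphate, magnesium, uric acid or cholesterol, and Section 5.0 treats Grade 3 or worse toxicity regardless of attribution. Long-standing abnormalities could therefore be counted as events. This stands, and the fix has to deal with it.

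**Conclusion.** The concern holds in a limited form. Criterion 7 and footnote 3 do not agree, and that rests on the text alone. The endpoint also takes in laboratory toxicities that the protocol names but does not schedule tests for, so silent events in phosphate, magnesium, uric acid, cholesterol, bilirubin or alkaline phosphatase would be missed by scheduled testing. The effect on the count can only be downward, towards an early stop or non-rejection. Its size cannot be estimated from the documents, and the probabilities in the illustration should not be read as an estimate. The conclusion assumes that footnote 3 is the complete order list, as its analyte-by-analyte form suggests, and that no unstated routine panel fills the gap. The remedy is cheap enough that the change should be made.

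**What to change.** 1. Reconcile criterion 7 with footnote 3 by adding total bilirubin and alkaline phosphatase to the panel at screening and on treatment.
2. Add phosphate and magnesium to the chemistry blood already drawn and, if the sponsor agrees, uric acid and cholesterol. Include a screening value for each.
3. State in the endpoint definition how a value already abnormal at screening is treated, so that new or worsened findings are told apart from pre-existing ones. The sponsor should also settle how the removal text applies to pre-existing findings.
4. For any named analyte left off, including urine protein, say in the endpoint definition and in the report that it was not assessed.

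The cost is assay charges, with no extra visit or needle-stick. The downside is a somewhat higher count of laboratory events, including pre-existing ones if step 3 is skipped. If the sponsor prefers not to add the optional assays, step 4 costs nothing and still prevents absence of testing from being read as absence of toxicity.
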